In addition to these **Specific Aims**, we will monitor subjects' MA use, as improvements in brain bioenergetics, mood/anxiety and may decrease MA usage. Therefore, we will record urine drug testing results, to determine whether creatine vs. placebo is associated with a greater number of MA-free tests during the 8 weeks of randomized treatment.

PARTICIPANT SELECTION CRITERIA

123 women will be randomly assigned in a 1:1 ratio to either creatine or placebo for eight weeks. Table 1 outlines eligibility criteria.

TABLE 1 INCLUSION AND EXCLUSION CRITERIA

INCLUSION CRITERIA:

- Female gender, ages 18-55 inclusive
- Current primary diagnosis of MA dependence or abuse, with MA preferred drug of abuse (Lifetime MA use > 20 grams)
- Current diagnosis of Major Depressive Disorder (MDD)
- Current HAMD score ≥ 10
- Clinical Global Impressions–Severity (CGI-S) depression score ≥ 4
- If taking a psychotropic medication for depressed mood, regimen must be stable for ≥ 4 weeks prior to randomization

EXCLUSION CRITERIA:

- Persons unable to provide adequate informed consent
- Persons who are at clinically significant suicidal or homicidal risk
- Primary substance-related diagnosis *other than* MA dependence or abuse
- Comorbid substance dependence diagnosis, other than nicotine (substance abuse diagnoses are not excluded)
- Positive pregnancy test, due to the unknown effects of MRI scanning on the unborn fetus
- Positive test for antibody to the Human Immunodeficiency Virus (HIV)
- History of renal disease
- Clinically significant medical or neurological illness identified by history, physical exam and laboratory testing
- Known or suspected intellectual disability, or developmental disorder, e.g. autism
- History of hypersensitivity reaction to creatine

WITHDRAWAL / EARLY TERMINATION CRITERIA:

- Withdrawal of informed consent
- Suicide attempt
- Psychiatric hospitalization
- Onset of bipolar disorder or psychotic disorder
- Positive pregnancy test
- Incarceration
- Inability to comply with study protocol

▪ Treatment with electroconvulsive therapy (ECT)▪ Increase in HAMD score > 25% from baseline▪ Serious adverse event

▪ HEALTHY CONTROL SUBJECTS:
 
▪ Female gender, ages 18-55 inclusive▪ No current or past DSM-5 diagnosis, as determined by clinical and structured interviews▪ No first-degree relatives with known or suspected DSM-5 diagnosis

DESIGN

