At the screening visit, an ECG will be conducted in order to examine the heart and ensure participant safety; an adult cardiologist will also evaluate all individuals during the screening phase. If during the MRI/MRS scans we unexpectedly discover something that warrants further inspection, we will refer the participant to her primary care provider for follow-up, along with the MRI/MRS report that shows the findings. Any costs related to following up on unexpected findings will be the responsibility of her and/or her insurance provider. In conjunction with the brain scans performed pre- and post-treatment, a brief battery of cognitive tests will be administered, to evaluate change associated with creatine or placebo. Trained psychometricians administer tests on the day of scanning. Scoring is done blind to subjects' group status, clinical ratings and imaging results. The cognitive testing battery instruments were

chosen because they are sensitive to frontal lobe integrity: the Wisconsin Card Sorting Task (WCST)[129], the Stroop Color-Word Test[130, 131], and the Wechsler Memory Scale (WMS-IV)[132]. Furthermore, the WCST[133], Stroop Test[134] and WMS-IV [90] each have been associated with performance deficits in MA users.

TABLE 2A Schedule of Procedures for Methamphetamine-dependent Females												
	Screening	Treatment Phase								Follow Up Phase		
Study Week →	-2 to 0^a	1*	2*	3*	4*	5*	6*	7*	8*	9	10	11
Informed Consent, Demographics	X											
Medical History & Physical Exam, ECG	X											
Hematology & Chemistries	X									X		
Phlebotomy for Creatinine Levels	X				X					X		
HIV	X											
Pregnancy Test and vital signs	X	X	X	X	X	X	X	X	X	X	X	X
PRISM Diagnostic Interview	X											
ASI	X									X		
Randomization to Creatine or Placebo	X											
Treatment with Creatine or Placebo		X	X	X	X	X	X	X	X			
Urine Drug Screen / Other Drug Use	X	X	X	X	X	X	X	X	X	X	X	X
Concomitant Medications	X	X	X	X	X	X	X	X	X	X	X	X
Food Frequency Questionnaire	X									X		
Cognitive Tests: WCST, STROOP and WMS-IV (with WASI vocabulary)***	X									X		
Adverse Events		X	X	X	X	X	X	X	X	X	X	X
Treatment Program Attendance	X	X	X	X	X	X	X	X	X	X	X	X
Clinical Scales: HAMD**, BAI**, CGI-S**, C-SSRS	X	X	X	X	X	X	X	X	X	X	X	X

³¹ P-MRS and ¹ H-MRS****	X									X		
*During the 8 Treatment Weeks, MA Subjects Have 2 Study Visits Per Week (separated by \geq 48 hours)												
**Procedure will be collected at one of the twice weekly visits												

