- During the intake and assessment interview, participants may become emotionally upset when asked about their psychiatric history including suicide attempts, or physical and sexual abuse.
- There is a 50% chance that the participant will be assigned to placebo, in which they will not receive creatine.
- Participants may experience discomfort or swelling when blood is drawn for laboratory tests. Rarely, infection can result from blood draws.
- It is possible that the participant's illness could worsen during the study. This could be related or unrelated to the study. Individuals with Major Depressive Disorder are at risk for depression, suicidal ideation, and suicide attempts as part of their illness. If the participant's illness worsens to the point that the study doctor considers them a danger to themselves or others, they will be hospitalized. If the participant is hospitalized they will be withdrawn from the study. In the event of hospitalization, the participant or the participant's insurance company will be responsible for the associated costs.
- It is possible that treatment with creatine will not be effective for the participant's depression, and that study participation will therefore delay the start of effective treatment.
- The researchers will take precautions to safeguard the participant's confidentiality, but it is possible that a breach of confidentiality could occur. A Certificate of Confidentiality has been obtained for this study.
- The participants may experience gastrointestinal discomfort as a result of taking study medication. We recommend taking the study medication with food to reduce possible stomach discomfort.
- MRI/MRS scans do not use ionizing radiation like x-rays or CT scans. Instead, magnetic fields and radio waves are used to take the pictures. There are no known risks related to MRI scans – other than the risk of injury when metallic objects are brought into the scanning room by mistake. Serious injury can occur during an MRI scan to persons who have:
 - Cardiac (heart) pacemakers.
 - Metal clips on blood vessels (also called stents).
 - Artificial heart valves.
 - Artificial arms, hands, legs, etc.
 - Brain stimulator devices.
 - Implanted drug pumps.
 - Cochlear [6] implants.
 - Ocular [118] implants or known metal fragments in eyes.
 - Exposure to shrapnel or metal fillings
 - Other metallic surgical parts.
 - Orthodontic braces on the teeth.
 - Body jewelry or piercings that cannot be removed for the scan.

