 - i. Reporting to the University of Utah Institutional Review Board. If a protocol violation/deviation meets one or more of the following criteria, the PI will submit the violation/deviation via ERICA within 10 working days from the time the investigator learns of the event.
 - Intended to eliminate apparent immediate hazard to a research participant; or
 - Harmful (caused possible harm to participants or others, or places them at increased risk of harm – including physical, psychological, economic, or social harm, such as breach of confidentiality); or
 - Possible serious or continued noncompliance (such as a deviation that has happened previously and is now being repeated).
 - ii. Reporting to the Food and Drug Administration. Protocol violations/deviations will be summarized in the annual IND report.

Trial Stopping Rules

In our open-label study of 5 grams of daily creatine for 8-weeks, there were no unanticipated problems or SAEs reported. Considering this is a feasibility study of double-blind, placebo-controlled creatine at the same dose as our open-label study, and the open-label creatine was well tolerated with a low side effect profile, we have not adopted rules for stopping the study. We have, however, developed criteria for early termination of participants and the criteria are listed below:

- Suicide attempt
- Psychiatric hospitalization

- Onset of bipolar disorder or psychotic disorder
- Positive pregnancy test
- Incarceration
- Inability to comply with the study protocol

IMAGING METHODS AND DATA ANALYSIS

1. Neuroimaging Protocol

i. Magnetic Resonance Imaging (Siemens Trio 3T MRI system)

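### A woman hospitalised for psychiatric worsening before week 9 leaves the study, not only the study drug, so the plan as written gives her no post-drug safety assessments

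*Combined protocol and SAP*

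**What the plan says.** The section on risks and benefits describes a woman whose illness worsens until the study doctor judges her dangerous to herself or to someone else. She is to be admitted, and then: "If the participant is hospitalized they will be withdrawn from the study". The same paragraph recognises the underlying hazard: "Individuals with Major Depressive Disorder are at risk for depression, suicidal ideation, and suicide attempts as part of their illness".

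Table 1 puts psychiatric hospitalisation in a single list of ten events headed "WITHDRAWAL / EARLY TERMINATION CRITERIA". Withdrawn consent stands there beside suicide attempt, onset of bipolar or psychotic disorder, positive pregnancy test and serious adverse event (SAE). The list does not separate events that stop the drug from events that end participation. The section on trial stopping rules repeats six of the ten, with this introduction: "we have not adopted rules for stopping the study. We have, however, developed criteria for early termination of participants".

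Table 2A schedules screening, treatment weeks 1 to 8 and a "Follow Up Phase" at weeks 9 to 11. It has no early-termination column, and none of its footnotes deals with a woman who stops early.

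**The concern.** The women covered by the hospitalisation rule are those with the worst psychiatric course on treatment. Three weeks of off-drug C-SSRS and adverse-event assessment are planned, but the rule takes these women out before any of it if they are admitted during treatment. The trial record would then have no scheduled observation of later suicidality or of how the event resolved, and no laboratory values at drug stop. The safety data for weeks 9 to 11 would describe a group from which women hospitalised during treatment had been removed.

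The plan relies on individual termination criteria and has no trial-level stopping rules, so what happens to a woman after termination needs to be defined.

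**Working it through.** The plan states no figure on this point, so the check is a count of scheduled assessments.

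**Inputs, all from Table 2A (methamphetamine-dependent women)**
- Drug is given in weeks 1 to 8. Post-drug weeks are 9, 10 and 11.
- Adverse events, C-SSRS and pregnancy test are marked in every week from 1 to 11. Post-drug assessments: 3, taking one visit a week, because the twice-weekly footnote covers only the treatment weeks.
- "Hematology & Chemistries": screening and week 9. Post-baseline panels: 1.
- "Phlebotomy for Creatinine Levels": screening, week 4 and week 9. Post-baseline draws: 2.
- Footnote on visit frequency: "During the 8 Treatment Weeks, MA Subjects Have 2 Study Visits Per Week". On-drug visits: 8 × 2 = 16 at most.
- Footnotes: five (one to four asterisks, and a). Footnotes on early stopping: 0. Two of them let a woman stay in the study without cognitive testing or without a scan, so partial participation is allowed for, but not after a safety event.

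**Count for a hospitalised woman if the rule is followed as written**

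| Hospitalised | Post-drug AE, C-SSRS, pregnancy | Post-baseline creatinine | Post-baseline hematology and chemistries |
|---|---|---|---|
| Before the week-4 draw | 0 of 3 | 0 of 2 | 0 of 1 |
| After the week-4 draw, before week 9 | 0 of 3 | 1 of 2 | 0 of 1 |
| After the week-9 visit | 1 of 3 | 2 of 2 | 1 of 1 |
| After the week-10 visit | 2 of 3 | 2 of 2 | 1 of 1 |

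**Does another section restore the follow-up?** The data safety monitoring plan sets reporting duties to the IRB, FDA and NIDA but no visit or test after withdrawal. The section on control of the investigational drug makes a general commitment to FDA rules for IND studies and names no assessment for a withdrawn woman. No section says that a woman may stop drug and remain in follow-up.

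**The case against.** The strongest reply is that most of this is silence, not a rule. Table 2A does not reserve weeks 9 to 11 for completers, and nothing forbids following a woman who has stopped. The only explicit study-exit wording is one sentence in a risk disclosure. That stands for every Table 1 event except hospitalisation. A reader might infer that suicide attempt, psychotic or bipolar onset, pregnancy and SAEs all end follow-up too. The documents do not support this: the headings speak of withdrawal and early termination without saying from what. For hospitalisation the reply fails, because the sentence says that she leaves the study.

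A reader might also infer that the event is lost or the woman left without care. Neither follows. She is an inpatient when study visits stop. SAEs go to NIDA within 15 calendar days, and FDA may ask for more data on an IND safety report. (The protocol does not define an SAE; that a psychiatric admission counts as one is an assumption.) Before stopping she has two visits a week, with adverse events, C-SSRS, pregnancy test and vital signs in each treatment week. What is missing is planned research follow-up afterwards, not acute care or notification.

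Few women may be affected. Table 1 excludes women at marked suicidal or homicidal risk at entry, and the sponsor's open-label study at the same dose and duration reported no SAEs. This is fair, although the size of that study is not given. It limits how often the gap matters but does not close it. The consent form, which might describe follow-up after withdrawal, is not in the public documents.

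**Conclusion.** The point holds for hospitalisation: a woman admitted for psychiatric worsening before week 9 is taken out of the study, and with that go all three post-drug safety assessments, the only post-baseline hematology and chemistry panel, and the end-of-drug creatinine. For the remaining Table 1 events the finding is narrower: the plan leaves open whether drug or participation ends, and the counts apply to them only if termination is read as study exit.

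The size is per woman. The documents give no hospitalisation rate, and the 20% attrition assumed for sample size covers all causes, so the number affected cannot be derived. The conclusion rests on the rule being followed as written, on one visit a week in weeks 9 to 11, and on the unseen consent form not providing otherwise. It is an inexpensive improvement to safety follow-up in the women at highest psychiatric risk. It is not evidence that harm would go unreported.

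**What to change.** Change the sentence in the risk section to say that hospitalisation ends study drug, and that safety follow-up continues unless consent is withdrawn or the woman cannot be reached. Add a Table 2A footnote for women stopped early for a safety event: the week-9 safety laboratory tests at or near drug stop where feasible, then the three weekly adverse-event and C-SSRS contacts, by telephone if needed, with a pregnancy test where applicable. A woman hospitalised after the week-9 visit keeps her remaining contacts. Which Table 1 events end study drug can stay with the sponsor.

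Cost against the plan as written: at most 1 laboratory visit + 3 weekly contacts = 4 per woman who stops before week 9; 3 − 1 = 2 for a woman hospitalised after the week-9 visit; 3 − 2 = 1 after the week-10 visit. The assessments are already in Table 2A; telephone contact is new. These women may be hard to reach, and the data safety monitoring plan requires IRB and FDA approval and NIDA agreement before the change takes effect.

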Spectroscopy will be analyzed using Liner Combination of Model Spectra (LCModel) [135], which analyzes an *in vivo* spectrum as a linear combination of model *in vitro* spectra from individual metabolite solutions. This model is fully automatic and user independent. A nearly model-free constrained regularization method is used for convolution and baseline. For quantification, absolute metabolite concentrations (institutional units) will be estimated using the unsuppressed water signal as an internal concentration reference. Also, total creatine levels will be used as a denominator for calculating the relative concentration for the comparison with previous reports. The standard Siemens libraries of model metabolite spectra provided with LCModel will be used in the basis set. The metabolites from the basis set will include alanine, aspartate, creatine, gamma-amino butyric acid, glucose, glutamine, glutamate, glycerophosphocholine, glutathione, myo-inositol, scyllo-inositol, lactate, N-acetylaspartate, N-

acetylaspartylglutamate, phosphocholine, phosphocreatine, phosphoethanolamine, scyllo-inositol, and taurine. For the reliability of detection, the Cramer-Rao lower bounds (CRLB) will be determined: the acceptable upper limit of estimated standard deviations will be set at 20% [136].

Post processing of ^{31}P -MRS data will be conducted using jMRUI software (jMRUI v. 4.0, European Community) with the AMARES algorithm (Advanced Method for Accurate, Robust and Efficient Spectral fitting of MRS data with use of prior knowledge). Before fitting the FID (Free-induction-decay) data, a Hamming filter will be applied to reduce signal contamination from neighboring voxels, with apodization of 10 Hz line broadening. Fourier transformation, frequency shifts correction, and zero-order/first order phase correction as well as baseline correction will be applied. The structural image-processing tool FSL (FMRIB Software Library, Release 4.1, The University of Oxford) will be used to account for gray matter, white matter, and cerebrospinal fluid (CSF), in order to correct the partial volume effects on metabolite concentrations. The MRS grid will be positioned over the images in an identical fashion between baseline and treatment scans for each participant. The peak area for each ^{31}P -MRS metabolite will be calculated as a percentage of the total phosphorus signal.

Overall Analytic Strategy: The analyses proposed are generalized estimating equations (GEE) regression modeling, which will be used for our longitudinal data analyses with group comparison across treatment visits for the variables of metabolite levels, depression/anxiety symptoms, and cognitive tests. GEE allows robust estimations of standard errors and permits adjustment for time-varying covariates. We assume that measurements made closer in time are more correlated than those made farther apart. Thus, first-order autoregressive structure is assumed. For our repeated measurement data, GEE fits a population-averaged model with working correlation structure to statistically evaluate the time effect of creatine supplementation. We will control for age, other drug abuse, anxiety scores, and tissue partial volume effects in each GEE model. Sidak multiple comparison procedure will be employed to adjust for family wise error (FWE) rate. The Sidak tests make conservative controls of FWE, giving slightly smaller adjusted p-values than the Bonferroni correction.

Overall Power and Sample Size Calculations: For this pilot study, considering a 20% attrition rate, 95 participants will be recruited to achieve a sample size of 75. To determine the minimum effect that would likely be detected with a sample size of 75, a power analysis was performed. Effect for the power analysis was specified as average baseline (over two measures) HAM-D scores compared with average HAM-D scores during active treatment (over eight measures). A gradual onset of effect during active treatment is assumed, starting with an effect of 0 and ending with an effect of 0.5, resulting in an average effect during treatment of 0.25. The effect to be tested was treated as a linear combination of the separate measures (y^*), and a pattern of correlation of 0.5 was used. This generated a standard deviation [105] for y^* that will be different from the within-occasion SD for Y itself. Then the effect magnitude specified was divided by the $SD(y^*)$ to generate an "effective" or de facto effect size, which resulted in an effect size of 1.09 with a power of 0.87.

Statistical Analysis for Specific Aim 3: Cognitive testing data with a repeated measures design will evaluate the cognitive improvement after 8 weeks of creatine supplementation, specifically in executive and working memory deficits, found in MA users. The relative improvements on WCST, Stroop and WMS-IV scores associated with creatine versus placebo will be tested conservatively with the assumption of independence among comparisons. Independent variables include a time variable of "visit" (baseline and 8 weeks of treatment), creatine" (placebo or creatine group), and an interaction term, "creatine \times visit", where a significant interaction will indicate significant differences between treatments. The depression effect will be

tested by stratifying depressed and non-depressed MA users. Power and Sample Size Calculations: Previous reports, meta-analysis, and our preliminary data suggest that the cognitive deficits of MA users have medium-to-large (0.5 to 0.8) effect size, especially in the episodic memory, compared to healthy subjects. Thus, the proposed sample size (n=76) will have enough power (> 80%) based on Cohen's guidelines with adjusted Sidak p-values of 0.0169. [137, 138]

ADMINISTRATIVE RESPONSIBILITIES

Resources:

The facilities at the University of Utah that are available for the proposed research include the following: the Brain Institute, Assessment and Referral Services and UNI. The Brain Institute currently occupies 5,900 square feet of office and laboratory space in a building in the University of Utah Research Park adjacent to the Health Sciences campus. It also occupies clinical space in UNI, the site of the Brain Institute's PRISMA 3T MRI research scanner. Assessment and Referral Services [4] is a freestanding clinic within the Department of Psychiatry. It occupies 6000 square feet in downtown Salt Lake City close to public transportation and approximately three miles from the University of Utah. It consists of 20 full time staff and approximately 30 part time staff. Salt Lake Behavioral Health Services contracts with ARS to provide three different functions. One is to provide assessments and referrals for individuals in Salt Lake County who have been arrested for driving under the influence; or who are seeking substance abuse services voluntarily or due to other court mandates. The third is to provide Interim Group Services (IGS), which are free groups for individuals awaiting Salt Lake County funded substance abuse treatment services.

Recruitment of Participants:

Primarily, participants will be recruited from ARS. Staff at ARS will refer women who identify methamphetamine as their primary drug of choice to the study staff. In addition, women will be recruited from the Clinical Assessment Center (CAC) at UNI. Staff at CAC will contact members of the study team to inform them if a MA-using woman interested in participating. The study team member will then follow-up with the interested woman to arrange a screening assessment.

Study information flyers will also be hung at ARS, 12-step recovery program meeting locations, Fellowship Hall, other drug-use referral locations, and public transportation such as buses and trax. Additionally, participants will be recruited by radio advertisements on select radio stations in the Salt Lake City area.

Study details will also be available on utahbrain.org.

CONTROL OF INVESTIGATIONAL DRUG

The University of Utah Research Pharmacy will prepare and dispense the creatine/placebo. They will dispense the study medication in a blinded fashion to a study team member, and it will be stored at room temperature in a locked office that is accessible only to research personnel. The study will be conducted in compliance with all applicable FDA regulations for IND studies.

The blind will be broken following the culmination of the study or at the request of a medical professional dealing with a medical emergency in a case in which it would help a study participant. The Research Pharmacy will be contacted in order to break the blind.

DATA COLLECTION, MANAGEMENT AND PROTECTED HEALTH INFORMATION

The study team will create case report forms (CRFs) for data collection. The consent, permission and assent forms, CRFs, laboratory results, radiology reports, MRI registration forms, and other necessary documents will be filed in each study participant's binder. Study participant binders will contain protected health information such as name, date of birth, age, address, and phone number. Binders will be stored in locked cabinets located in locked offices. Only essential study team members will have access to participant binders.

Using a password-protected computer with access limited to study personnel, the research team will maintain a computerized screening and enrollment log. Participant screening, eligibility status, and consent for participation status will be recorded in this log. Before the performance of any study procedures, potential participants (and where applicable their parent(s) or guardians(s)), verbal and written informed consent will be obtained. When a participant is screened for study eligibility, they will be assigned a screening ID number. The individual will maintain the screening ID until they have completed the first scanning visit. If a subject is determined to be ineligible during screening, the reason for the screen failure will be recorded on the computerized screening and enrollment log. Once a subject has completed screening enrolled for study participation, they will be assigned a subject ID number, which will be used to identify all of the data collected from them during the study.

Data from CRFs will be entered into SPSS. No personal identifiers from study participants will be entered into SPSS. Forms that have missing or inconsistent data will be recorded in the database; however a "missing data" code will be entered in place of each piece of missing or inconsistent data. Two study team members -- the individual who enters the data, and a second individual monitoring data entry -- will check each CRF form entered into SPSS for accuracy and completeness.

RECORD RETENTION

In keeping with 21CFR312.57, study records will be maintained for at least two years after the drug is approved by the FDA or after shipment and delivery of the drug for investigational use has ceased and the FDA has been notified.

BIBLIOGRAPHY

1. Darke, S., et al., *Major physical and psychological harms of methamphetamine use*. Drug and alcohol review, 2008. 27(3): p. 253-62.
2. Sato, M., *A lasting vulnerability to psychosis in patients with previous methamphetamine psychosis*. Ann N Y Acad Sci, 1992. 654: p. 160-70.
3. Zweben, J.E., et al., *Psychiatric symptoms in methamphetamine users*. The American journal on addictions / American Academy of Psychiatrists in Alcoholism and Addictions, 2004. 13(2): p. 181-90.
4. Marshall, B.D. and D. Werb, *Health outcomes associated with methamphetamine use among young people: a systematic review*. Addiction, 2010. 105(6): p. 991-1002.
5. Callaghan, R.C., et al., *All-cause mortality among individuals with disorders related to the use of methamphetamine: A comparative cohort study*. Drug and alcohol dependence, 2012.
6. Elkashef, A., et al., *The NIDA Methamphetamine Clinical Trials Group: a strategy to increase clinical trials research capacity*. Addiction, 2007. 102 Suppl 1: p. 107-13.
7. Xi, Z.X. and E.L. Gardner, *Hypothesis-driven medication discovery for the treatment of psychostimulant addiction*. Current drug abuse reviews, 2008. 1(3): p. 303-27.
8. Davidson, C., et al., *Methamphetamine neurotoxicity: necrotic and apoptotic mechanisms and relevance to human abuse and treatment*. Brain research. Brain research reviews, 2001. 36(1): p. 1-22.
9. Garwood, E.R., et al., *Amphetamine exposure is elevated in Parkinson's disease*. Neurotoxicology, 2006. 27(6): p. 1003-6.
10. Guilarte, T.R., *Is methamphetamine abuse a risk factor in parkinsonism?* Neurotoxicology, 2001. 22(6): p. 725-31.

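### GEE tests are planned with no small-sample correction or t/F reference: a slight excess of false positives for Aims 1 and 3, and a material one for Aim 2 if weekly visits are tested as categories

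*Combined protocol and SAP*

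**What the plan says.** The Overall Analytic Strategy applies GEE to "group comparison across treatment visits for the variables of metabolite levels, depression/anxiety symptoms, and cognitive tests", which covers the outcomes of all three aims. On inference it says that "GEE allows robust estimations of standard errors and permits adjustment for time-varying covariates". For the working correlation, "first-order autoregressive structure is assumed". For covariates, "We will control for age, other drug abuse, anxiety scores, and tissue partial volume effects in each GEE model". Family-wise error is to be handled by Sidak adjustment. No section names a bias-corrected covariance, a t or F reference distribution, or a model-based alternative.

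A creatine-by-visit term is written out only for Aim 3, "where a significant interaction will indicate significant differences between treatments". Visit there has two levels, baseline and week 8. The Neuroimaging Protocol also gives two scans per woman for Aim 1. In Table 2A the HAMD and BAI (Aim 2) are collected weekly, but the plan does not say whether visit enters those models as a category or as a linear term.

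The number of women differs between sections. Overall Power and Sample Size Calculations says "95 participants will be recruited to achieve a sample size of 75", "considering a 20% attrition rate". The Aim 3 section uses 76. Study Procedures puts 47 women, half of the total, on placebo, which implies 94. Participant Selection Criteria says "123 women will be randomly assigned in a 1:1 ratio to either creatine or placebo for eight weeks". The footnotes to Table 2A let a woman skip cognitive testing or enter the study without being scanned, and give no expected numbers.

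**The concern.** The sandwich variance with a normal or chi-square reference is justified when there are many independent clusters. Here each woman is a cluster, and the planned number is 75 to 123. At that size the uncorrected variance is slightly low on average. More importantly, a chi-square reference treats the estimated covariance matrix as if it were known. The second problem grows with the number of parameters tested together.

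The Sidak adjustment controls family-wise error only if each test delivers its nominal level. If the Aim 2 tests reject too often, the adjusted p-values inherit the excess, and a chance difference in depression or anxiety could be reported as an effect of creatine.

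**Working it through.** **Inputs.** From the documents: GEE, robust standard errors, AR(1) working correlation and four covariates (Overall Analytic Strategy); 75 completers and 20% attrition (power section); 123 randomised (Participant Selection Criteria); two visits for Aims 1 and 3; weekly scales over eight treatment weeks (Table 2A); Sidak level 0.0169 (Aim 3 section). Assumed: normal outcomes, an overall two-sided 5% level, an uncorrected Wald chi-square test, and the true correlations given below.

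**The plan's own figures.** Sidak for three tests at 5% is 1 - 0.95^(1/3) = 0.01695, so 0.0169 is consistent with an overall 5% level. 75/(1 - 0.20) = 93.75, or 94, against the stated 95. 123 x 0.80 = 98.4. The plan states no true type I error, so there is none to reproduce.

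**Closed form, one degree of freedom.** With two visits and no covariates, the creatine-by-visit coefficient is the difference between arms in mean change. With n per arm, the uncorrected sandwich variance is (n - 1)/n times the unbiased one. The true rejection rate is therefore P(|t| > z x sqrt((n - 1)/n)) on 2n - 2 degrees of freedom.
- 75 women (n = 37.5): 1.96 x sqrt(36.5/37.5) = 1.934 on 73 df, giving 5.7%. At 0.0169 the rate is 2.1%.
- 123 women (n = 61.5): 1.944 on 121 df, giving 5.4%. At 0.0169 the rate is 1.9%.
- 60 and 40 women (assumed shortfalls): 5.9% and 6.4%.

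**Closed form, eight degrees of freedom.** Baseline plus eight weeks gives nine visit levels, hence 8 df for a categorical interaction. The 5% chi-square cut-off is 15.51. With nu = 2n - 2, Hotelling's result gives the true rate as P(F > 15.51 x (n - 1)/n x (nu - 7)/(8 nu)) on 8 and nu - 7 df.
- 75 women: 15.51 x 36.5/37.5 = 15.09, and 15.09 x 66/584 = 1.706. P(F(8,66) > 1.706) = 11.4%.
- 123 women: 15.26 x 114/968 = 1.797. P(F(8,114) > 1.797) = 8.5%.

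If the factor (n - 1)/n is dropped, so that the covariance is unbiased but the reference is still chi-square, the 75-woman figure falls only to 10.3%. Most of the excess therefore comes from the reference distribution.

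**Simulation under the null.** GEE with AR(1) working correlation, four covariates (one time-varying), equal arms, and true correlation either exchangeable 0.5 or AR(1) 0.7. The Monte Carlo standard error is about 0.2-0.7 points at nominal 5%. The last column uses a Kauermann-Carroll covariance with an F reference.

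| Test (nominal level) | 75 women, uncorrected | 123 women, uncorrected | 75 women, corrected |
|---|---|---|---|
| Two visits, 1 df (5%) | 5.7-6.0% | 5.3% | 4.7-5.1% |
| Two visits, 1 df (0.0169) | 1.9-2.2% | 1.9% | 1.4-1.8% |
| Nine visits, linear time, 1 df (5%) | 5.9% | 5.3% | 5.0% |
| Nine visits, categorical, 8 df (5%) | 10.4-11.5% | 8.5-8.6% | 4.3-4.7% |
| Nine visits, categorical, 8 df (0.0169) | 4.7-5.3% | 3.5-4.0% | 1.3-2.0% |

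Further results:
- A separate simulation with three baseline covariates gave 12.3% for the 8-df test with 38 and 37 women. Across simulations the range with 75 women is therefore about 10-12%.
- With 94 randomised and 20% dropout the 8-df rate was 11.1%.
- Two-visit rates were 6.5% with 40 women and 6.9% with 60 (2.6% and 2.9% at 0.0169). The 60-woman run was high even after correction (6.0%), which suggests simulation noise.
- The robust standard error of a single coefficient with 75 women was 0.97-1.00 of the true value.
- For the 8-df test with 75 women, a Mancl-DeRouen covariance kept with chi-square still gave 8.4-9.1%. With an F reference it gave 3.7-4.1%.

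**The case against.** The strongest reply is that the plan does not contain the test with the large error. The only interaction it writes out has two visits and one degree of freedom. The power section describes the HAM-D effect as a single combination of measures, mean on treatment against mean at baseline, which points away from an omnibus test. For every test that is clearly specified, the excess is under one percentage point with 75 women. The trial is described as a pilot and a feasibility study, and GEE uses partial data from women who drop out, so 75 may understate the information. The plan also names no reference distribution, so an uncorrected chi-square test is an inference from silence.

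Much of this stands. A reader might infer that standard errors are materially too small across all aims. The figures do not support that: the shortfall for one coefficient is at most about 3% with 75 women. A reader might also infer that the plan prescribes a test that doubles the error rate. The documents do not support that either, because the Aim 2 analysis is left open and the categorical test is only one reading of it.

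The reply does not remove the gap. The power section is not an analysis specification. Comparing groups across weekly visits, in the interaction form written for Aim 3, can naturally be read as categorical. On that reading the error stays near 8.5% even with 123 women.

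**Conclusion.** The concern holds in limited form, and the fix is a cheap improvement. The plan's GEE inference is anti-conservative at every sample size the documents give. For Aims 1 and 3 this is minor: about 5.7-6.0% at nominal 5% and about 2% at 0.0169 with 75 women, and 5.3-5.4% at nominal 5% with 123. It would be about 6-7% if omitted scans or cognitive tests left 40-60 women, a range that is assumed. For Aim 2 it is material only if visit is categorical and the interaction is tested as a block.

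In that case the tempting explanation, that standard errors are too small and so p-values too low, is mostly wrong. The main cause is the chi-square reference, and correcting the covariance alone does not cure it. All sizes rest on the assumptions of a Wald chi-square test, an overall two-sided 5% level, normal outcomes and the chosen correlations.

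**What to change.** In the Overall Analytic Strategy:
1. Prespecify a one-degree-of-freedom contrast for Aim 2. An example is the difference between arms in mean on-treatment minus baseline HAMD, which matches the time profile in the power section; the BAI can be treated likewise. State how visit enters the model.
2. State that GEE inference uses a bias-corrected sandwich variance, for example Kauermann-Carroll, together with t or F reference distributions. Both parts are needed for any test with several degrees of freedom. A repeated-measures mixed model with Kenward-Roger degrees of freedom is an alternative.
3. Reconcile the number of women (75, 76, 94, 95 and 123), because the size of the correction depends on it.

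The cost is a few sentences and a software option, with slightly wider intervals and slightly larger p-values. The documents name SPSS for data entry but no analysis software, so check that the chosen package offers the correction. Trial conduct and data collection do not change.
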